### **5.5 Criteria for Taking a Participant Off Protocol Therapy**

Duration of therapy will depend on individual response, evidence of disease progression and tolerance. In the absence of treatment delays due to adverse event(s), treatment may continue until one of the following criteria applies:

- Disease progression
- Intercurrent illness that prevents further administration of treatment
- Unacceptable adverse event(s)
- Participant demonstrates an inability or unwillingness to comply with the oral medication regimen and/or documentation requirements
- Participant decides to withdraw from the protocol therapy
- Investigator determines a change of therapy would be in the best interest of the subject
- Female subject becomes pregnant
- General or specific changes in the participant's condition render the participant unacceptable for further treatment in the judgment of the treating investigator
- Study Termination

Participants will be removed from the protocol therapy when any of these criteria apply. The reason for removal from protocol therapy, and the date the participant was removed, must be documented in the case report form (CRF). Alternative care options will be discussed with the participant.

An ODC Treatment Ended/Off Study Form will be filled out when a participant is removed from protocol therapy. This form can be found on the DF/HCC website at <http://www.dfhcc.harvard.edu/research/clinical-research-support/document-library-forms-sops-etc/>.

In the event of unusual or life-threatening complications, treating investigators must immediately notify the Overall PI, [REDACTED]

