## **5.7 Criteria for Taking a Participant Off Study**

Participants will be removed from study when any of the following criteria apply:

- Lost to follow-up
- Withdrawal of consent for data submission
- Death

The reason for taking a participant off study, and the date the participant was removed, must be documented in the case report form (CRF).

For Decentralized Subject Registrations, the research team updates the relevant Off Treatment/Off Study information in OnCore.

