### 6.1 TAK-228 Dose Modifications

TAK-228 administration should be withheld for treatment-related adverse events that are Grade 3 or higher, despite supportive treatment per standard clinical practice. If the event resolves to Grade 1 or Grade 2 for hyperglycemia or rash or to baseline values within 2 weeks of interrupting treatment, then the subject may resume study treatment at a dose reduced by 1 level (see Table below). If study drug administration is delayed for more than 4 weeks (28 consecutive days) due to non-resolving study drug-related grade 3 toxicity despite supportive treatment per standard clinical practice, or more than 3 dose reductions of study drug are required in a subject, then study drug treatment should be stopped, the subject discontinued from the study, and the EOT visit completed within 30 days ( $\pm 7$ ) after the last dose of study drug.

If study drug administration is delayed for more than 6 weeks (42 consecutive days) due to non-treatment related adverse events, then study drug treatment should be discontinued, and EOT visit completed within 30 days ( $\pm 7$  days) after the last dose of study drug

If study drug is delayed for either less than 4 weeks (28 consecutive days) due to non-resolving study drug-related grade 3 toxicity or less than 6 weeks (42 consecutive days) due to non-treatment related adverse events, subjects should skip the dosing cycles missed and when if treatment is resume, this should be at the next scheduled dosing cycle.

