### 6.3 Management of Clinical Events

#### 6.3.1 Management of Hyperglycemia

Guidance for TAK-228 dose management in the event of hyperglycemia is provided in the table below.

Table 5: Management of Hyperglycemia

Grade	Description	Treatment	TAK-228 Dose Modification
1	Fasting blood sugar > ULN–160 mg/dL	Continue close monitoring of blood sugars. Consider initiation of oral hypoglycemic agent and/or insulin if not well controlled on oral agent.	None.
2	Fasting blood sugar > 160–250 mg/dL	Initiate oral hypoglycemic agent and/or insulin if not well controlled on oral agent.	None.
≥3	Fasting blood sugar > 250 mg/dL	Initiate oral hypoglycemic agent and/or insulin.	Hold drugs until ≤ Grade 2. Resume TAK-228 based on timing of recovery: ≤ 1 week: resume at same dose and schedule; >1 but ≤2 weeks: reduce TAK-228 by 1 dose level >2 weeks: discontinue subject from study

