### 6.3.5 Management of Rash

Guidance for TAK-228 dose adjustment for the event of rash is provided in the table below

Table 9: Management of Rash

Grade	Description	Treatment	TAK-228 Dose Modification
≤ 2	Macules/papules covering ≤ 30% body surface area with or without symptoms	Consider treatment with topical steroid cream/ointment and/or oral anti-histamines or antibiotics.	None.
≥ 3	Macules/papules covering > 30% body surface area with or without symptoms	Consider treatment with topical steroid cream/ointment, oral antihistamines, oral antibiotics, and/or pulsed steroids.	Hold until ≤ Grade 2; Resume TAK-228 based on timing of recovery and severity of symptoms: ≤ 3 weeks: reduce dose by 1 dose level; > 3 weeks and severely symptomatic: stop TAK-228 and discontinue subject from the study.

Subjects who develop Grade 4 rash should permanently discontinue study treatment, unless they derive clinical benefit as determined by the site investigator, in which case they may be retreated at a reduced dose level after recover to ≤ Grade 1 severity. Grade 4 rash is defined as rash acneiform and/or papulopustular with papules and/or pustules covering any % body surface area, which may or may not be associated with symptoms of pruritus or tenderness, AND are associated with extensive superinfection requiring with intravenous (IV) antibiotics indicated; life threatening consequences (NCI CTCAE Version 4.03, effective date 14 June 2010).

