### 6.3.8 Management of Aspartate Aminotransferase/Alanine Aminotransferase Elevations

Table 14: Management of Aspartate Aminotransferase/Alanine Aminotransferase Elevations

Grade	Description	Treatment	Dose Modification
1	>ULN to 3×ULN	None	None
2	Asymptomatic with levels 3 to 5×ULN; >3×ULN with the appearance of worsening fatigue, nausea, vomiting, right upper quadrant pain or tenderness, fever, rash, or eosinophilia.	
 
Closely monitor LFTs at least weekly or more frequently as indicated.
 
Assess subject for other causes of transaminitis (eg, past medical history, concomitant medications).
 
	None
3	>5 to 20×ULN; >5×ULN for >2 weeks	Same as for Grade 2.	Hold TAK-228 until ≤Grade 1; Restart TAK-228 at the same dose. Permanently discontinue study treatment if in combination with Grade 2 total bilirubin elevation when alternative causes cannot be identified (ie, Hy's Law);
4	>20×ULN	Same as for Grade 2.	Stop TAK-228 and discontinue subject from the study.

Table 14: Management of Aspartate Aminotransferase/Alanine Aminotransferase Elevations

Grade	Description	Treatment	Dose Modification
			Permanently discontinue study treatment if in combination with Grade 2 total bilirubin elevation when alternative causes cannot be identified (ie, Hy's Law).

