#### **7.4 Long Term Follow-up Evaluations**

After a subject discontinues from study treatment, they will continue to be followed for survival and subsequent anti-cancer therapy every 6 months until death or 2 years after study treatment discontinuation. Follow up may be accomplished via clinic visit, phone call, or other avenues as appropriate.

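### Four toxicity clauses in Section 6 take subjects off the study where Sections 5.5, 5.6, 5.7 and 7.4 imply off treatment only, so survival follow-up for that subset depends on which text a site follows

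*Combined protocol and SAP*

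**What the plan says.** Four clauses remove the subject from the study:

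- Section 6.1, for a delay of more than 4 weeks due to drug-related Grade 3 toxicity or more than 3 dose reductions: drug is stopped, "the subject discontinued from the study, and the EOT visit completed within 30 days".
- Table 5 (Section 6.3.1), Grade 3 or higher hyperglycemia: ">2 weeks: discontinue subject from study".
- Table 9 (Section 6.3.5), Grade 3 or higher rash with slow recovery and severe symptoms: "stop TAK-228 and discontinue subject from the study".
- Table 14 (Section 6.3.8), Grade 4 AST/ALT: "Stop TAK-228 and discontinue subject from the study".

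The sections that govern study status and follow-up read differently. Section 5.7 opens "Participants will be removed from study when any of the following criteria apply" and lists loss to follow-up, withdrawal of consent for data submission, and death. Section 5.5 places unacceptable adverse events among the reasons for leaving protocol therapy. Section 7.4 says of subjects who stop study treatment that "they will continue to be followed for survival and subsequent anti-cancer therapy every 6 months until death or 2 years after study treatment discontinuation". Section 5.6 and study calendar footnote 14 give the same schedule. None of the three makes an exception for toxicity.

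**The concern.** Leaving treatment and leaving the study have different consequences. Someone off treatment is contacted every 6 months for survival and next-line therapy; someone off study need not be. Section 5.7 has the off-study date and reason recorded, and Section 5.8 labels a subject who ends study participation early a dropout. A site acting on Section 6 therefore has an administrative route to close the record.

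OS is a secondary endpoint, censored at the date last known alive (Section 12.2.2) and summarized by Kaplan-Meier (Section 12.4.2). Kaplan-Meier assumes that censored subjects have the same later risk as those still followed. Censoring because a subject could not tolerate the drug may break that assumption. Data on subsequent therapy would be lost for the same subjects. The trial is multicenter, so sites could resolve the conflict differently.

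**Working it through.** **Step 1: sort the rules that end treatment for an adverse event by what they end.**

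| Rule | Ends |
|---|---|
| 6.1, drug-related delay over 4 weeks or more than 3 reductions | drug and study |
| Table 5, hyperglycemia | study |
| Table 9, rash | drug and study |
| Table 14, Grade 4 AST/ALT | drug and study |
| 6.1, non-treatment-related delay over 6 weeks | treatment |
| Table 6, pneumonitis | treatment |
| Table 8, Grade 4 mucositis | treatment |
| Table 11, left ventricular dysfunction | treatment |
| Table 12, QTc prolongation | treatment |
| Hy's Law note under Table 14 | treatment |
| Table 13, other Grade 4 non-hematologic toxicity | treatment |

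The conflict is confined to the first four rows. Subjects stopping under the others stay in survival follow-up on any reading. The 6.1 clause is the broadest of the four, since it is not tied to one toxicity.

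**Step 2: which endpoints are exposed.** Section 12.2.1 counts response only up to progression or cessation of trial therapy. Study status after the drug stops cannot change it, so ORR, the stage 1 rule and the sample size stand. OS and subsequent-therapy data are exposed.

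**Step 3: illustrate the size for OS.** The plan gives no figure to reproduce. Every input here is an assumption: exponential survival with a 12-month median in the other subjects, so λ = ln 2 / 12 = 0.0578 per month; a fraction f removed at month 2; hazard hλ in that fraction throughout.

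- True survival: S(t) = (1 − f)·exp(−λt) + f·exp(−hλt). The true median solves S(t) = 0.5.
- With removal at month 2, only subjects with hazard λ remain at risk, so the large-sample Kaplan-Meier median is 2 + ln(S(2)/0.5)/λ.

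Example, f = 20%, h = 2: S(2) = 0.7127 + 0.1587 = 0.8715. The Kaplan-Meier median is 2 + ln(0.8715/0.5)/0.0578 = 2 + 9.62 = 11.62 months. The true median is 10.37 months (0.4395 + 0.0604 ≈ 0.50). The difference is 1.25 months.

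Kaplan-Meier median minus true median, in months:

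| f (of 40 subjects) | h = 0.75 | h = 1 | h = 1.5 | h = 2 |
|---|---|---|---|---|
| 2.5% (1) | −0.07 | 0 | 0.10 | 0.17 |
| 5% (2) | −0.14 | 0 | 0.20 | 0.33 |
| 10% (4) | −0.28 | 0 | 0.40 | 0.65 |
| 20% (8) | −0.58 | 0 | 0.78 | 1.25 |
| 25% (10) | −0.74 | 0 | 0.96 | 1.53 |

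If the hazard rises only after the stop, the 10-25% range at h = 1.5 to 2 becomes 0.42 to 1.73, and the top of the 5% row is about 0.4.

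**The case against.** The strongest case against is that this is loose wording that no careful site would act on. Much of that stands. Sections 5.6 and 7.4 are as literal as Section 6, carry no exception, and are the sections that govern follow-up. Section 5.6 continues adverse-event follow-up even after discontinuation from the study, so the phrase does not end all contact in this protocol. Section 6.1 schedules the same end-of-treatment visit for subjects who only stop drug. The Grade 4 cell of Table 14 uses both forms of words. Section 5.7 does not say that its list is exhaustive, and the list omits completion of the 2-year follow-up. Lost survival follow-up is thus one of two available readings.

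The objection does not remove the conflict. In Section 6.1 and Tables 9 and 14, stopping drug and leaving the study are separate instructions, and most neighbouring rules give only the first. A site could take the difference as meant.

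Three stronger readings are tempting, and the documents support none of them:

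- That follow-up ends for everyone who stops for toxicity. Most toxicity rules end treatment only.
- That the plan deliberately treats drug-related stops differently from unrelated ones. The two delay rules in Section 6.1 suggest this, but pneumonitis, mucositis, cardiac and other toxicity stops are also worded as treatment only.
- That the OS median would be biased upward. This needs a worse prognosis in the removed subjects, which no document states.

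The assumed 10-25% may also be high for four clauses. Section 6.3.1 says hyperglycemia has not been dose-limiting since early treatment became standard, which weakens the Table 5 route. And with 40 uncensored subjects and a 12-month exponential median, the central 90% sampling range of the observed median is about 8.1 to 17.0 months, wider than any shift shown.

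**Conclusion.** The contradiction is on the page and should be reconciled. Its reach is the subset stopping under Section 6.1's drug-related clause or Tables 5, 9 and 14. Early OS censoring in that subset is a risk created by conflicting text; it is not a certain result of following the protocol.

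The size cannot be derived from the documents, which give neither the share of subjects affected nor their prognosis. Under the stated assumptions and a hazard ratio of 1.5 to 2, the OS median is overstated by about 0.1-0.4 months with 1-2 of 40 subjects removed and 0.4-1.5 months with 4-10 removed. At a hazard ratio of 1 there is no shift; below 1 the median is understated. These are scenarios, not estimates. OS is a secondary, single-arm estimate without a test. The point matters because follow-up ended early may not be recoverable and each record counts among 40.

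**What to change.** In Section 6.1 and in Tables 5, 9 and 14, replace the words that discontinue the subject from the study with: *discontinued from protocol therapy and followed per Sections 5.6 and 7.4*. Leave untouched every threshold and rule on when drug is held, reduced or stopped; this point takes no view on those.

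The cost is wording in four places. No new visits or procedures are needed, because Section 5.6 already plans survival follow-up by phone and record review. If subjects have already been taken off study under one of these clauses, check whether their survival follow-up continued and, where consent allows, restore it.

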### 6.2 Dose Levels for Dose Reductions

**Table 4: Dose Modifications for Single-Agent TAK-228**

Dose Level	Dose Regimen	TAK-228 Capsules: Number and Strength
Starting Dose Level	30 mg QW	Six 5-mg capsules
-1	20 mg QW	Four 5-mg capsules
-2	15 mg QW	Three 5-mg capsule
-3	10 mg QW	Two 5-mg capsules

QW=once weekly.

It is not mandatory to hold treatment in the absence of optimal supportive care for toxicities of nausea and diarrhea. Optimal supportive care is defined as an anti-emetic regimen that employs a 5-HT3 antagonist. If nausea and diarrhea persist despite optimal supportive care, treatment should be held until the subject returns to baseline.

In the case that a patient experiences persistent grade 1 or 2 toxicity, treatment with TAK-228 may be withheld at the discretion of the treating investigator. Once toxicity resolves in the case of grade 1 toxicity or resolves or at least improves to grade 1 in the case of grade 2 toxicity, treatment with TAK-228 may be resumed at the current dose level. If persistent grade 1 or 2 toxicity recurs, treatment with TAK-228 can again be held withheld at the discretion of the treating investigator. Once toxicity resolves in the case of grade 1 toxicity or resolves or at least improves to grade 1 in the case of grade 2 toxicity, treatment with TAK-228 may be resumed but at a reduced dose by one level.

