### 6.3.6 Management of Nausea and/or Vomiting

Guidance for TAK-228 dose adjustment for the event of nausea and/or vomiting is provided in the table below.

Table 10: Management of Nausea and/or Vomiting

Grade	Description	Treatment	TAK-228 Dose Modification
≤ 2	Loss of appetite with or without decreased oral intake; 1-5 episodes of vomiting within 24 hours	Maximize anti-emetic therapy; Consider IV fluid hydration.	None.
≥ 3	Inadequate oral intake; ≥ 6 episodes of vomiting within 24 hours	Maximize anti-emetic therapy; Initiate tube feeding, IVF, or TPN.	If experienced for ≤72 hours, hold TAK-228 until ≤ Grade 1, then resume TAK-228 without dose modification. If experienced for >72 hours despite optimal therapy, hold TAK-228 until ≤ Grade 1, then resume treatment with the dose of TAK-228 reduced by 1 level.

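### Section 6.2 judges supportive care for diarrhea by an anti-emetic, and its baseline restart for severe nausea disagrees with Table 10

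*Combined protocol and SAP*

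**What the plan says.** Section 6.1 withholds TAK-228 for treatment-related events of Grade 3 or higher that occur despite usual supportive treatment. Its condition for resuming one dose level lower is: "If the event resolves to Grade 1 or Grade 2 for hyperglycemia or rash or to baseline values within 2 weeks of interrupting treatment".

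Section 6.2, below the dose-level table, adds three sentences on nausea and diarrhea:

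- One sets the standard of care for both toxicities: "Optimal supportive care is defined as an anti-emetic regimen that employs a 5-HT3 antagonist".
- Another makes a hold optional where that standard has not been met: "It is not mandatory to hold treatment in the absence of optimal supportive care for toxicities of nausea and diarrhea".
- The last covers symptoms that continue although it has been met: "If nausea and diarrhea persist despite optimal supportive care, treatment should be held until the subject returns to baseline".

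None of the three names a grade or a restart dose. The next paragraph of 6.2 deals with persistent Grade 1 or 2 toxicity, for which "treatment with TAK-228 may be withheld at the discretion of the treating investigator".

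Table 10 (Section 6.3.6) covers nausea and vomiting. At Grade 2 or lower the advice is "Maximize anti-emetic therapy; Consider IV fluid hydration", with no dose modification. At Grade 3 or higher there are two branches. For the shorter events the rule is "If experienced for ≤72 hours, hold TAK-228 until ≤ Grade 1, then resume TAK-228 without dose modification". For the longer ones it is "If experienced for >72 hours despite optimal therapy, hold TAK-228 until ≤ Grade 1", after which the dose goes down one level.

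Diarrhea has no table of its own. It falls to Table 13 (Section 6.3.9), the residual table for other non-hematologic toxicities. That table holds Grade 3 or higher events, and Grade 2 events that become intolerable, until Grade 1 or lower. The Grade 3 or higher restart is one level down. No sentence in Section 6 ranks 6.1, 6.2 and the tables in 6.3.

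**The concern.** Nausea, vomiting and diarrhea are all on the protocol's list of the commonest treatment-emergent events (Section 11.1.1.1), and safety and tolerability is a secondary endpoint (Section 12.2.2). The hold rules for these events will therefore be consulted, and at more than one institution.

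An anti-emetic is the wrong yardstick for diarrhea. Sections 5.1 and 6.3.6 both name anti-diarrheals as a separate class of supportive medication, yet the 6.2 definition leaves them out. Section 5.1.1 recommends a 5-HT3 antagonist before dosing, so a subject treated as recommended meets the 6.2 definition whether or not the diarrhea has been treated.

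For severe nausea the plan gives two restart thresholds. Two sites could follow the protocol and dose the same subject differently. What is at stake is safety and consistent exposure.

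**Working it through.** The plan states no figure on this point, so the check compares the rules. Section 6.2 is given its most favorable reading, as an elaboration of the Grade 3 trigger in 6.1.

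| Rule | Toxicity named | Condition on prior care | Restart threshold | Restart dose |
|---|---|---|---|---|
| 6.1 | any related event | usual supportive treatment | Grade 1 or baseline, or baseline only (see step 3) | one level down |
| 6.2 | nausea and diarrhea | 5-HT3 anti-emetic regimen | baseline | not stated |
| Table 10, 72 hours or less | nausea/vomiting | none | Grade 1 or lower | same dose |
| Table 10, more than 72 hours | nausea/vomiting | optimal therapy | Grade 1 or lower | one level down |
| Table 13, Grade 3 or higher | diarrhea, as a residual toxicity | none | Grade 1 or lower | one level down |

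**Step 1: diarrhea and the definition.** Take a subject with Grade 3 diarrhea on a full anti-diarrheal regimen and no 5-HT3 antagonist. Under 6.2 optimal care is absent, so a hold is not mandatory. Under 6.1 the event is Grade 3 despite supportive treatment, so the drug is withheld. Table 13 also holds. Now take a subject given only ondansetron before dosing. Under 6.2 this subject has had optimal care for diarrhea without receiving any anti-diarrheal.

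**Step 2: nausea and the restart.** Inputs: baseline Grade 0; Grade 3 nausea for more than 72 hours despite optimal therapy, at 30 mg; down to Grade 1 on the next weekly dosing day; one level below 30 mg is 20 mg (Table 4).

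- Table 10: Grade 1 meets the threshold, so the dose is 20 mg.
- 6.2: Grade 1 is not baseline, so the dose is 0 mg.
- Weekly doses per cycle: 28 / 7 = 4. Each week spent at Grade 1 therefore changes 1 of 4 doses.

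This example is illustrative. It assumes that restart is allowed on the next weekly dosing day. The last paragraph of 6.1 says that missed dosing cycles are skipped and treatment resumes at the next one. If cycle there means 28 days, the 20 mg versus 0 mg contrast need not arise on that day, but the two thresholds still differ.

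**Step 3: which side 6.1 takes.** Its restart clause can be parsed in two ways. Either Grade 1 suffices for any event, with Grade 2 allowed for hyperglycemia and rash, or the grades apply only to hyperglycemia and rash and everything else must return to baseline. The first reading agrees with Table 10, the second with 6.2. The text does not settle it, so 6.1 is not counted for either side.

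**The case against.** The strongest reply is that the sentence in 6.2 makes sense in context. 6.1 has just set the trigger at Grade 3 or higher, and the following paragraph of 6.2 handles Grade 1 and 2 separately. The missing grade is then largely supplied. That stands. A reader might infer that 6.2 forces a hold for any persistent Grade 1 or 2 nausea, against the discretion given in its next paragraph. The Grade 3 reading is the more natural one, and the point does not depend on the other.

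A reader might also infer that 6.2 is the lone outlier among four rules. The documents do not support this, because 6.1 is ambiguous. Nor is the diarrhea restart conflict as firm as the one for nausea. Table 13 does not name diarrhea, and a rule that names the toxicity might be taken to prevail over a residual table.

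The practical effect may be small. Dosing is weekly and the mean plasma half-life is about 8 hours (Section 10.1), so symptoms that last to the next dose may be uncommon. For the same reason, it matters little that Table 10 sets no care condition for an event of 72 hours or less. A subject whose baseline is already Grade 1 meets no restart conflict at all.

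Finally, baseline may have been intended. In that case Table 10 is the text to change. The inconsistency remains either way.

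**Conclusion.** Minor, and wrong as written. Two errors survive the favorable reading: the anti-emetic test of optimal care for diarrhea, and the unresolved difference between baseline (6.2) and Grade 1 or lower (Table 10) for Grade 3 or higher nausea. For diarrhea the same restart mismatch exists with Table 13, but only in its residual role.

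The documents give no rates by grade, so the number of subjects affected is unknown. A reader might infer a bias in the response rate through lost doses. Nothing in the documents supports that, and the sample size and decision rule are untouched.

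**What to change.** In Section 6.2:

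1. Keep the 5-HT3 definition for nausea and vomiting, and define optimal supportive care for diarrhea as an anti-diarrheal regimen.
2. Limit the sentence that makes a hold non-mandatory to Grade 2 or lower.
3. Replace the baseline sentence with: *For Grade 3 or higher nausea/vomiting or diarrhea, hold and resume per Table 10 (nausea/vomiting) or Table 13 (diarrhea).*
4. State that, for nausea/vomiting and diarrhea only, these tables govern over 6.1 and 6.2. Retain both the Table 13 hold for intolerable Grade 2 diarrhea and the discretionary Grade 1 or 2 hold in 6.2.

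The precedence sentence is narrow on purpose. A general one would also change other toxicities, such as rash, where Table 9 allows 3 weeks for recovery and 6.1 allows 2.

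The cost is amendment wording, with no change to visits, sample size or analysis. The downside is that a subject may restart at Grade 1 rather than at baseline, as Table 10 already permits. If the sponsor intended baseline, it should amend Table 10 instead, so that a single threshold applies.
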